2. To compare type 1 and 3 immunogenicity of one or three doses of bOPV with the same number of doses of bOPV co-administered with nOPV2.
3. To assess the presence of fecal viral shedding (as determined by real-time RT-PCR) over time following one dose of nOPV2, bOPV, or co-administered nOPV2 and bOPV.
4. To estimate household transmission of nOPV2 by assessing the presence of fecal viral shedding (as determined by real-time RT-PCR) among siblings of vaccine recipients.
5. To assess the occurrence and genomic characteristics of intertypic recombinants in stool specimens of vaccine recipients and siblings after one dose of nOPV2 given with or without bOPV.

Methods:

This is an open-label randomized clinical trial. Vaccine recipient participants will be enrolled and randomized at 6 weeks to one of three arms:

- A: nOPV2 @ 6, 10, and 14 weeks
- B: nOPV2 + bOPV @ 6, 10, and 14 weeks
- C: bOPV @ 6, 10, and 14 weeks

For each vaccine recipient, a sibling below 10 years of age will be selected for participation as a sibling.

Outcome measures/variables:

Poliovirus antibody titers to types 1, 2 and 3 will be measured in sera extracted from vaccine recipient blood collected at 6, 10, 14, and 18 weeks. Antibody titers at 6 weeks of age will be the assumed starting point for the expected decline in maternal antibody assuming a half-life of 28 days. Shedding of poliovirus will be measured from stool specimens collected from vaccine recipients and one sibling each at 1, 2, and 4 weeks post-vaccination in Arm A and at 2 and 4 weeks post-vaccination in Arms B and C. Intertypic recombinants will be characterized in a subset of stool specimens collected from vaccine recipients and siblings.

Description of the Research Project

Hypothesis to be tested:

Does this research proposal involve testing of hypothesis: No Yes (describe below)

Primary hypotheses to be tested are:

1. Type 2 immune response after two doses of nOPV2 with bOPV is non-inferior to the immune response observed after two doses of nOPV2 given alone (10% non-inferiority margin).
[Primary objective: 1]
2. Type 1 and 3 immune responses after two doses of bOPV with nOPV2 are non-inferior to the immune responses observed after two doses of bOPV given alone (10% non-inferiority margin).
[Primary objective: 2]

Secondary hypotheses to be tested are:

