5. The vaccine recipient will receive the recommended routine childhood vaccinations, except polio vaccination. Routine polio vaccines will be replaced by the study vaccine.
6. Schedule the next visit.

Study Clinic Visit – 14 weeks of age [All arms]

During this visit, the following procedures will be conducted:

1. The medical officer will complete the eCRF and examine the vaccine recipient.
2. One blood specimen (1 ml) will be collected by venipuncture.
3. Study vaccines will be administered, as directed by study arm.
4. The vaccine recipient will be observed for 30 minutes to monitor for any adverse reactions to the study vaccine.
5. The vaccine recipient will receive the recommended routine childhood vaccinations, except polio vaccination. Routine polio vaccines will be replaced by the study vaccine.
6. Schedule the next visit.

Study Clinic Visit – 18 weeks of age [All arms]

During this visit, the following procedures will be conducted:

1. The medical officer will complete the eCRF and examine the vaccine recipient.
2. One blood specimen (1 ml) will be collected by venipuncture.
3. Completion of study activities.
4. Vaccine recipients in Arms A and B will be given the first of three bOPV doses. Note: Arm B will be given three doses of bOPV to account for possible immunologic interference during co-administration of bOPV with nOPV2. All vaccine recipients will be given the first of two fIPV doses.

Timing of Evaluations

Entry/eligibility evaluations

- Entry evaluations will be completed at 6 weeks of age.
- Blood collection and study vaccine administration are planned during the study entry evaluation at 6 weeks of age. Blood will be collected before administration of any study vaccines. On the date of enrolment, study vaccines will be administered only if adequate blood specimen has been collected. If blood cannot be collected on the day of enrolment, study vaccine recipients will be discontinued from the study.
- The window for entry evaluation including collection of blood and administration of vaccine is 42–48 days of age.

Post-entry evaluations and follow-up

- After the first enrolment visit (6 weeks of age, range 42–48 days), the window for study visits is +/- 3 days.
- Blood will be collected before any study or EPI vaccines are administered.
- Stool collection from vaccine recipients and one sibling each will take place at 8 and 10 weeks of age for all Arms, and additionally at 7 weeks for Arm A only.

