who become seropositive ($\geq 1:8$) (seroconversion) or vaccine recipients who demonstrate at least a four-fold increase in titer (boosting). Baseline maternal antibody titer will be determined at 6 weeks of age and the estimated maternal antibody level at each blood collection will be calculated assuming an exponential decline with a half-life of 28 days. Vaccine recipients and siblings will be categorized for shedding poliovirus through results from multiple real-time PCR (rRT-PCR) assay designed to detect poliovirus. Household transmission will be defined as present if siblings test positive for nOPV2 vaccine virus at either 1, 2, or 4 weeks following the vaccine recipient's vaccination at 6 weeks of age. nOPV2 vaccine virus in stool specimens from vaccine recipients and siblings will be further characterized through high-resolution Illumina RNA sequencing. Intertypic vaccine-derived recombinants will be characterized in stool collected from study vaccine recipients and siblings.

Randomization

Vaccine recipients will be randomized to one of three arms using a block randomization scheme. The randomization algorithm will be generated by CDC staff and executed in REDCap. The randomization algorithm will not be known to study staff in icddr,b. Randomization assignment will be revealed after completing enrolment procedures, when study staff "click" on randomization button on the study tablets. Therefore, study staff enrolling and managing vaccine recipients will not have *a priori* knowledge of randomization scheme. As this is an open-label trial, the arm assignment of vaccine recipients will be known to study staff and the vaccine recipient's parents after randomization. Laboratory staff processing blood samples in Bangladesh will not have *a priori* knowledge of randomization scheme but will know the arm assignment after randomization. However, CDC laboratory staff testing for poliovirus antibody titers will remain blinded throughout the study.

Timeline of activities

Activities	Year 1 (months)					
	2	4	6	8	10	12
Protocol development/IRB approval, Staff training/site preparation						
Enrolment						
Start and completion of vaccination						
Follow up of vaccine recipients						
Lab testing						
Dissemination/Publications						

Data Analysis

General Issues

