This is an open-label, non-inferiority, randomized clinical trial that will compare immune response to types 1, 2 and 3 polioviruses of nOPV2 and bOPV when co-administered compared to nOPV2 and bOPV given alone. The study will recruit 795 vaccine recipients in three arms. Vaccine recipients will be enrolled at 6 weeks of age and followed until 18 weeks of age, for 12 weeks of follow-up. For each vaccine recipient enrolled, one sibling will be enrolled at the same time and followed for 4 weeks .

General Analytical Issues

The data will be analysed by study investigators that include epidemiologists and statisticians. Statistical packages that will be used for the analysis include R, SAS and STATA.

For assessing immunity to polio, seropositivity is defined as reciprocal polio neutralizing antibody titers

of at least 1:8. Immune response will be defined as either seronegative vaccine recipients ($<1:8$ titers) who become seropositive ($\geq 1:8$) [seroconversion] or vaccine recipients who demonstrate a four-fold

increase in titer (boosting). Baseline maternal antibody titers will be determined at 6 weeks of age and the estimated maternal antibody level at each blood collection will be calculated assuming an exponential decline with a half-life of 28 days.

For assessing fecal viral shedding, detection of nOPV2 or bOPV vaccine virus in stool specimens from vaccine recipient or sibling at either 1, 2, or 4 weeks post-vaccination of the vaccine recipient at 6 weeks of age will be defined as positive for viral shedding. For assessing the detection of household transmission, presence of transmission will be defined as the sibling of the vaccine recipient testing positive for nOPV2 vaccine virus at either 1, 2, or 4 weeks post-vaccination of the vaccine recipient at 6 weeks of age.

To characterize the intertypic recombinants in a subset of stool specimens of vaccine recipients and siblings after one dose of nOPV2 given with or without bOPV, amplicon sequences from long-read sequencing methods will be used to confirm genome structure. Amplicon sequences will also be mapped against all three Sabin vaccine reference sequences to generate coverage plots.

Primary Analytical Approach

The primary analytical approach will be intention-to-treat. To evaluate the primary objectives, the intention-to-treat analysis will be restricted to vaccine recipients who:

- Have not withdrawn consent for receipt of vaccines and follow-up evaluations since enrolment.

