- Vaccine recipient received the scheduled study vaccination at 6 weeks of age.

Table 5: Study arms comparison, study endpoints, and results by objective

Study Objective	Study Arms Comparison	Endpoint (vaccine recipient age)	Results Included in Analysis
Primary			
1. To compare type 2 immunogenicity of two doses of nOPV2 with two doses of nOPV2 co-administered with bOPV.	A vs. B	14 weeks	Serology: 6, 10, 14 weeks
2. To compare type 1 and 3 immunogenicity of two doses of bOPV with two doses of bOPV co-administered with nOPV2.	C vs. B	14 weeks	Serology: 6, 10, 14 weeks
Secondary			
1. To compare type 2 immunogenicity of one or three doses of nOPV2 with the same number of doses of nOPV2 co-administered with bOPV.	A vs. B	10 weeks	Serology: 6, 10 weeks
		18 weeks	Serology: 6, 10, 14, 18 weeks
2. To compare type 1 and 3 immunogenicity of one or three doses of bOPV with the same number of doses of bOPV co-administered with nOPV2.	C vs. B	10 weeks	Serology: 6, 10 weeks
		18 weeks	Serology: 6, 10, 14, 18 weeks
3. To assess the presence of fecal viral shedding (as determined by real-time RT-PCR) over time following one dose of nOPV2, bOPV, or co-administered nOPV2 and bOPV.	Descriptive with comparisons of A vs. B and B vs. C	10 weeks (i.e. 4 weeks post-vaccination)	Stool: 7 (Arm A only), 8, 10 weeks from vaccine recipient
4. To estimate household transmission of nOPV2 by assessing the presence of fecal viral shedding (as determined by real-time RT-PCR) among siblings of vaccine recipients.	Descriptive	10 weeks (i.e. 4 weeks post-vaccination)	Stool: 7 (Arm A only), 8, 10 weeks from sibling
5. To assess the occurrence and genomic characteristics of intertypic recombinants in stool specimens of vaccine recipients and siblings after one dose of nOPV2 given with or without bOPV.	Descriptive with comparison of A vs. B	10 weeks (i.e. 4 weeks post-vaccination)	Stool: 8, 10 weeks from vaccine recipient and sibling

Adverse Events (AEs)

Safety will be assessed by:

- Incidence rate of solicited systemic AEs 24–48 hours after the first study vaccination.
- Incidence rate of unsolicited AEs during entire study period.
- Incidence rate of serious AEs during entire study period.

Data Safety Monitoring Plan (DSMP)

Records to be kept

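### Secondary objective 3: the any-positive shedding rule gives Arm A three stools and Arm B two, so the named A vs B comparison is expected to favour Arm A even when type 2 shedding is equal

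*Protocol*

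**What the plan says.** - **Scoring rule.** Data Analysis, General Analytical Issues, gives one rule for all arms: shedding is positive if nOPV2 or bOPV virus is detected in stool from the "vaccine recipient or sibling at either 1, 2, or 4 weeks post-vaccination of the vaccine recipient at 6 weeks of age".
- **Stool schedule.** The Project Summary has stools collected "at 1, 2, and 4 weeks post-vaccination in Arm A and at 2 and 4 weeks post-vaccination in Arms B and C". Timing of Evaluations agrees: "8 and 10 weeks of age for all Arms, and additionally at 7 weeks for Arm A only".
- **Table 5, objective 3.** The arms-comparison column reads "Descriptive with comparisons of A vs. B and B vs. C". The results included are "Stool: 7 (Arm A only), 8, 10 weeks from vaccine recipient". The endpoint column gives 10 weeks of age.
- **Table 5, objective 4.** The stools are "Stool: 7 (Arm A only), 8, 10 weeks from sibling", and the comparison column says descriptive only. Outcome variables uses the same pooled rule: "Household transmission will be defined as present if siblings test positive for nOPV2 vaccine virus at either 1, 2, or 4 weeks".
- **Table 5, objective 5.** The A vs B comparison of recombinants uses "Stool: 8, 10 weeks from vaccine recipient and sibling", which is the same set in both arms.

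Nothing in the protocol limits the objective 3 A vs B comparison to the visits that both arms share.

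**The concern.** An ever-positive outcome depends on how often and when a child is sampled. Under the stated rule an Arm A infant has three chances to be positive and an Arm B infant has two, and Arm A's extra chance is the earliest post-dose sample. Randomisation does not balance this, because the difference lies in the measurement schedule. Scoring type 2 virus alone does not remove it either.

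The direction matters. The trial is justified by the need to learn whether co-administration inhibits either vaccine. Lower type 2 shedding in Arm B is what interference would look like, and unequal sampling alone would produce the same picture.

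**Working it through.** **The protocol's own figures.** It states no figure for the A vs B shedding comparison. Two related figures reproduce.
- Sample size: with 85% in both arms, a 10% margin, 90% power and one-sided 0.05, n = 2(0.85)(0.15)(1.645 + 1.282)² / 0.10² = 218.4. The continuity correction, (n/4)[1 + √(1 + 4/(0.10n))]², gives 237.96, so 238 per arm. Then 238/0.90 = 264.4, rounded up to 265.
- Day-14 shedding: the exact interval for 126/238 is 46.4% to 59.4%. The protocol gives 53% (46.4-59.5%).

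**Inputs.** w2 = 53% at 2 weeks comes from the Sample size section. The week-1 rate w1, the week-4 rate w4 and the within-child correlation are assumptions, because the protocol gives none of them. Both arms are given identical true type 2 rates.

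**The gap.** P(any of 3 positive) − P(any of 2 positive) = P(positive at week 1 and negative at weeks 2 and 4). This cannot be negative. It is zero only if no infant is positive at week 1 alone.

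**Limiting cases.**
- Positives fully nested in time: gap = max(w1, w2, w4) − max(w2, w4). With w1 at or below 53% and w4 below it, the gap is 0. With w1 = 60% it is 7 points.
- Independent stools: gap = w1(1 − w2)(1 − w4). With w1 = 60% and w4 = 30%, 0.60 × 0.47 × 0.70 = 0.197. Serial stools from one child are unlikely to be independent, so this is an extreme.

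**Between the extremes.** This uses a multivariate normal threshold model with common latent correlation ρ. The last column is the chance of nominal two-sided p<0.05 in favour of Arm A with 238 per arm.

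| w1 | w4 | ρ | Arm A | Arm B | Gap (points) | Chance p<0.05 |
|---|---|---|---|---|---|---|
| 45% | 30% | 0.9 | 57.2% | 53.7% | 3.4 | 11% |
| 53% | 30% | 0.9 | 60.3% | 53.7% | 6.6 | 31% |
| 53% | 30% | 0.7 | 67.0% | 57.0% | 10.1 | 62% |
| 53% | 30% | 0.5 | 72.5% | 60.0% | 12.4 | 82% |
| 60% | 40% | 0.7 | 71.5% | 60.1% | 11.4 | 75% |
| 70% | 30% | 0.5 | 80.2% | 60.0% | 20.2 | >99% |

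Over w1 of 45-70%, w4 of 30-40% and ρ of 0.5-0.9, the gap runs from about 3 to 20 points.

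**By size of gap.** For 60% vs 65%, the null standard error is √(2 × 0.625 × 0.375/238) = 0.0444 and the alternative one is √((0.65 × 0.35 + 0.60 × 0.40)/238) = 0.0443. The chance of p<0.05 is Φ[(0.05 − 1.96 × 0.0444)/0.0443] = 20%. With Arm B anywhere from 55% to 70%, a 5-point gap gives 20-23% and a 10-point gap gives 61-71%.

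**With matched stools.** Both arms then have the same P(any of 2 positive) when there is no interference. The expected gap is 0 and a two-sided 5% test returns to its nominal level.

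**The case against.** The best defence is that objective 3 asks for shedding over time and that Table 5 sets its endpoint at 10 weeks, a visit common to all arms. On that reading results would be shown visit by visit, which is unbiased at 8 and 10 weeks, and the rule in General Analytical Issues merely says which specimens count. A separate analysis plan, not seen here, might say so. That reading is possible, but the only stated definition is the pooled one, and the Table 5 row includes the Arm A-only stool beside a named A vs B comparison. An analyst who follows the text literally gets the bias.

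Three further points stand and limit the finding.
- Shedding is listed under exploratory questions, and no test or alpha is stated for it. The rejection rates above illustrate a test the protocol does not specify.
- The size rests on assumed week-1 and week-4 rates, and zero is within reach.
- A reader might infer that the household transmission comparison is biased in the same way. The protocol does not support that. Objective 4 is descriptive, plans no A vs B comparison and no pooling of Arms A and B, and its power discussion is built on Arm A alone. Using all three stools for an Arm A estimate is reasonable.

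**Conclusion.** The point holds for the objective 3 A vs B shedding comparison. As written, Arm A's type 2 ever-positive proportion is expected to exceed Arm B's by the share of infants positive only at week 1, with no interference at all. The direction follows from the definition. The size is conditional: 0 if no infant is positive at week 1 alone, and about 3 to 20 points under the assumed rates and correlations above.

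It would go too far to say that the trial will show lower shedding in Arm B, or to state a guaranteed minimum bias. Any positive floor depends on the chosen week-1 rate and correlation.

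B vs C is unaffected, because both arms have two stools. The primary immunogenicity endpoints, the sample size and objective 5 are also untouched. For objective 4 the only consequence is that sibling rates by arm, if shown under the same rule, are not directly comparable. This should be fixed before analysis; as a flaw in a secondary, exploratory objective, it does not threaten the trial's main conclusions.

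**What to change.** In General Analytical Issues and the Table 5 row for objective 3, state that the A vs B shedding comparison uses only the 8- and 10-week stools. Report each visit separately, plus an any-of-8-and-10-weeks summary among infants who have both stools. Report the 7-week Arm A results descriptively, outside the comparison. If sibling transmission rates are shown by arm, also give them on the 8- and 10-week stools; the Arm A estimate from all three stools can stay beside them.

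The cost is about one sentence and one table cell, with no new samples or visits. The downside is that the 7-week data do not enter the A vs B comparison, where Arm B has no counterpart to set against them.

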- Have adequate blood specimen for serological analysis from the enrolment visit at 6 weeks of age.
- Have adequate blood specimen for serological analysis from the follow-up visit as mentioned by arm by primary objective in Table 5.

For secondary objectives 1 and 2, the intention-to-treat analysis will be restricted to vaccine recipients who:

- Have not withdrawn consent for receipt of vaccines and follow-up evaluations since enrolment.
- Have adequate blood specimen for serological analysis from the enrolment visit.
- Have adequate blood specimen for serological analysis from the follow-up visit as mentioned by arm by secondary objective in Table 5.

For secondary objectives 3-5, the intention-to-treat analysis will be restricted to vaccine recipients and siblings who:

- Have not withdrawn consent for receipt of vaccines and follow-up evaluations since enrolment.
- Have adequate stool specimens to examine vaccine-virus particles.

Secondary Analytical Approach

In addition to an intention-to-treat analysis, we will also perform per protocol analysis. To evaluate the primary objectives, per protocol analysis will be limited to vaccine recipients with the same restrictions as that outlined in primary analytical approach for primary objectives with additional restrictions of:

- Adequate blood specimen for serological analysis within 3 days of the scheduled visit date. This applies to enrolment visit blood specimen as well as follow-up visit blood collection.
- Received all scheduled study vaccines within 3 days of scheduled visit date.

For secondary objectives 1 and 2, the per protocol analysis will be limited to vaccine recipients with the same restrictions as those outlined in the primary analytical approach for secondary objectives 1 and 2 with additional restrictions of:

- Adequate blood specimen for serological analysis within 3 days of the scheduled visit date. This applies to enrolment visit blood specimen as well as follow-up visit blood collection.
- Received all scheduled study vaccines within 3 days of scheduled visit date.

For secondary objectives 3-5, the per protocol analysis will be limited to vaccine recipients or siblings with the same restrictions as those outlined in the primary analytical approach for secondary objectives 3-5 with additional restrictions of:

- Adequate stool specimen to examine vaccine-virus particles within 3 days of the scheduled visit date.

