2b. Date of vaccination (dd/mm/yy): / /
3. Has any other child in the household received OPV since the last clinic visit ? Yes / No 3a. If yes, specify: _____
4. Has the child had diarrhea in the last 24 hours (≥ 3 loose stools in 24 hours)? Yes / No
4a. If yes, specify: duration of diarrhea in days:
(If the child currently has fever $>38.3^{\circ}\text{C}$, blood in stools, vomiting or signs of dehydration, do not continue with study procedures. Provide advice and referral as required.)
5. Has the child been sick since the last study visit? Yes / No 5a. If yes, specify: _____
6. Is the child on any immunosuppressive medications? Yes / No 6a. If yes, specify _____

Physical Exam

7. Temperature: . $^{\circ}\text{Celsius}$
8. Length #1: . cm
9. Length #2: . cm
10. Weight #1: . kg
11. Weight #2: . kg

Blood Collection

12. Blood sample collected? Yes / No 12a. If not, why? _____
13. Sufficient quantity (1 ml)? Yes / No 13a. If insufficient, why? _____
14. Time of collection (hh:mm): :

Vaccine Administration*If Study Arm A or B*

15. nOPV2 administered? Yes / No 15a. If not, reason: _____
If administered: 15b. Time of vaccine administration (hh:mm): :
15c. Expiration (mmm/yy): /

If Study Arm B or C

16. bOPV administered? Yes / No 16a. If not, reason: _____
If administered: 16b. Time of vaccine administration (hh:mm): :
16c. Expiration (mmm/yy): /

Clinic Visit at 10 weeks of Age (ctd.)

17. Pentavalent administered? Yes / No 17a. If not, reason: _____

If administered: 17b. Dose: Penta1 / Penta2 / Penta3

17c. Site of administration: Right thigh / Left thigh

18. PCV administered? Yes / No 18a. If not, reason: _____

If administered: 18b. Dose: PCV1 / PCV2 / PCV3

18c. Site of administration: Right thigh / Left thigh

Observe for 30 minutes after vaccine administration:

19. Any symptoms? Yes / No

19a. If yes, specify (*complete Adverse Event Form, if required*): _____

The following questions correspond to sibling of the study vaccine recipient. Note: the sibling does not need to be present for this visit.

20. Has the child received any poliovirus vaccines (bOPV, fIPV) since last visit? Yes / No

20a. If yes, specify: / /

20b. Date of vaccination (dd/mm/yy): _____

21. Has the child had diarrhea in the last 24 hours (≥ 3 loose stools in 24 hours)? Yes / No21a. If yes, specify: duration of diarrhea in days

22. Has the child been sick since the last study visit? Yes / No 22a. If yes, specify: _____

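### The two-dose non-inferiority claim is decided on a set with no dosing requirement, and the per-protocol set has only secondary rank; the direction of any bias depends on which vaccine was missed

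*Protocol*

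**What the plan says.** The first primary hypothesis (Hypothesis to be tested) reads in part "Type 2 immune response after two doses of nOPV2 with bOPV is non-inferior to the immune response", with two doses of nOPV2 alone as comparator and a 10% margin. The second hypothesis makes the matching claim for types 1 and 3 against bOPV alone.

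Under Data Analysis, Primary Analytical Approach, the protocol says "The primary analytical approach will be intention-to-treat". For the primary objectives it then narrows that set in three ways. One is that parents have not taken back their consent. Another is a usable baseline sample at 6 weeks. The last concerns later blood: infants must "Have adequate blood specimen for serological analysis from the follow-up visit as mentioned by arm by primary objective in Table 5".

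None of the three conditions concerns receipt of a study vaccine. That condition appears under Secondary Analytical Approach, which opens with "In addition to an intention-to-treat analysis, we will also perform per protocol analysis" and adds, among other restrictions, "Received all scheduled study vaccines within 3 days of scheduled visit date". The protocol does not say that the two analyses must agree.

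The clinic visit forms in Appendix A record the two vaccines separately. The 10-week form, for example, has "bOPV administered? Yes / No 16a. If not, reason". The Discontinuation Criteria remove infants given polio vaccine outside the study, but not infants who simply missed a study dose.

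**The concern.** The trial asks whether giving nOPV2 and bOPV together weakens the response to either. An Arm B infant who received only one of the two at a visit was not co-vaccinated at that visit, yet the deciding analysis counts that infant as if co-vaccination had taken place. In a superiority trial such dilution is usually conservative. In a non-inferiority trial it can move the arms together and help the claim. When the deciding set has no dosing condition, and the set that has one is ranked second, a false conclusion of no interference could stand on the first set alone.

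**Working it through.** **Inputs from the protocol.** Sample size section: margin 10 points; 238 evaluable per arm; assumed response 90% for type 2 and 85% for types 1 and 3; power 90%; alpha 0.05, sidedness not stated; attrition 10%. Table 5: type 2 is A versus B, types 1 and 3 are C versus B.

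**The plan's own figure.** At 85% in both arms, one-sided 5%:

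n = 2 × 0.85 × 0.15 × (1.645 + 1.282)² / 0.10² = 219 after rounding up.

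A continuity correction, (n/4) × [1 + √(1 + 4/(n × 0.10))]² with unrounded n, gives 238, the stated figure. One-sided 2.5% gives 268, or 288 with the correction. Enrolment: 238/0.90 = 264.4, so 265, as stated. One-sided 5% is used below, with 2.5% where it helps.

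**Assumptions not in the protocol.** A fraction f of Arm B received one vaccine without the other. For the serotype they did receive, these infants respond like the single-vaccine arm. For the serotypes they missed, they respond at 50%. The truth among co-vaccinated infants lies exactly at the margin.

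**Formula.** With control response C and observed Arm B response T:

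- SE = √[(C(1−C) + T(1−T))/238]
- false non-inferiority rate = Φ[(T − C + 0.10)/SE − 1.645]

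**Type 2, Arm B infants given nOPV2 without bOPV (C = 0.90, f = 5%).**

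- T = 0.95 × 0.80 + 0.05 × 0.90 = 0.805
- SE = √[(0.090 + 0.157)/238] = 0.0322
- rate = Φ(0.005/0.0322 − 1.645) = Φ(−1.490) = 6.8%

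**Types 1 and 3, the same infants (C = 0.85, f = 5%).**

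- T = 0.95 × 0.75 + 0.05 × 0.50 = 0.7375
- SE = √[(0.1275 + 0.1936)/238] = 0.0367
- rate = Φ(−0.0125/0.0367 − 1.645) = Φ(−1.985) = 2.4%

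With no true difference, T = 0.95 × 0.85 + 0.05 × 0.50 = 0.8325, and power for types 1 and 3 falls from 92% to 79%.

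False non-inferiority rate when Arm B infants lack bOPV:

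| f (assumed) | Type 2, one-sided 5% | Type 2, one-sided 2.5% | Types 1/3, one-sided 5% |
|---|---|---|---|
| 0 | 5.0% | 2.5% | 5.0% |
| 1% | 5.3% | 2.7% | not computed |
| 2% | 5.7% | 2.9% | 3.7% |
| 5% | 6.8% | 3.6% | 2.4% |
| 10% | 9.1% | 5.0% | 1.0% |

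**The opposite omission, bOPV without nOPV2.** The directions swap. Types 1 and 3 (85% versus 75%) rise to 5.6%, 6.6% and 8.6% at f = 2%, 5% and 10%. Type 2 falls to 3.4%, 1.8% and about 0.6%.

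**Whole visits missed.** Here the direction depends on the difference between arms after one dose, which the protocol does not state. Table 5 lists the 6-, 10- and 14-week serology as included for both primary objectives. If the specimen condition means all three bloods, an infant who missed the 10-week visit has no 10-week blood and is already out of the set. If it means only the 14-week endpoint blood, the infant stays in. The wording allows either reading.

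**The case against.** The case on the other side is substantial, and most of it limits the size of the point.

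- **Direction.** A reader might infer that the intention-to-treat set raises the error for all three serotypes. It does not. An infant who lacks bOPV favours the type 2 claim and works against the other two.
- **Size.** The figures that favour the claim assume a full single-vaccine response. An infant co-vaccinated at one of the two visits is still partly exposed to any interference, so for a given f they are upper bounds.
- **Frequency.** A yes/no field with a reason is routine on a form and is no evidence of a rate. Both vaccines are given in the clinic, in immediate sequence, so f may well be small.
- **Role of the per-protocol analysis.** A reader might infer that it has no bearing on the conclusion. The protocol says only that it is secondary. How discordant results are read may be settled in a statistical analysis plan that is not at hand.
- **Choice of set.** Excluding infants after randomisation in an open-label trial carries its own bias, so making the per-protocol set the only primary set would not be an improvement.

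What remains is a choice that the protocol itself makes. It ranks the two sets, and the one it puts first has no dosing condition for a hypothesis about two doses.

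**Conclusion.** The point holds in a limited form. The primary set can include infants who were not co-vaccinated, and the protocol lets a two-dose non-inferiority claim be declared on that set alone. For type 2, with Arm B infants given nOPV2 only, the one-sided 5% error rises by at most 0.7 points at f = 2%, 1.8 points at 5% and 4.1 points at 10%; at 1–2% it is under one point. These sizes rest on an assumed f and on a full single-vaccine response. The documents do not support a general claim that the analysis is biased towards non-inferiority. They support the narrower statement that the intention-to-treat set does not by itself reliably answer the co-administration question, in a direction that depends on which vaccine was missed.

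**What to change.** In the Primary and Secondary Analytical Approach sections, state that non-inferiority for each primary hypothesis is concluded only if the lower confidence limit for Arm B minus the comparator is above -10 points in both the intention-to-treat set and the per-protocol set already planned. State also that the per-protocol vaccine condition means the 6- and 10-week doses for the primary objectives, since the 14-week dose follows the endpoint blood; the 6-week dose for the one-dose hypotheses; and all three doses for the three-dose hypotheses.

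No new data, visits or analysis set are needed. The cost is some power. If the per-protocol set is an assumed 5% smaller (238 × 0.95 = 226 per arm), power per serotype at 85%, without continuity correction, falls from 92% to 91% at one-sided 5%, or from 86% to 85% (84.5%) at one-sided 2.5%. The loss is larger if deviations from the 3-day visit windows are common, because the 10% attrition allowance would then have to cover these as well as loss to follow-up.
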